### **3.5. Data Pooling**

Data from all study sites and countries will be pooled together for all analyses, unless otherwise specified.

### **3.6. Adjustments for Covariates**

Adjustments for covariates will be employed in the analysis of covariance (ANCOVA) and MMRM analyses. Any adjustments will be pre-specified in the description of the statistical analysis ([Section 4.4](#)).

### **3.7. Multiple Comparisons**

No adjustment for multiple comparisons is required for the primary efficacy endpoint. No p-value adjustments for multiple comparisons will be made for all other efficacy endpoints.

### **3.8. Subgroups**

The following subgroups may be used in selected data analyses. [Section 4.4](#) will describe the specific analyses to be performed for each subgroup.

- Age (< 65, 65 to < 75,  $\geq$  75 years)
- Race (White, Black/African-American, Asian, Other Races [i.e., American Indian or Alaska Native, Native Hawaiian or Other Pacific Islander, Multiple (more than 1 race category chosen), Other])
- BMI (< 25, 25 - < 30,  $\geq$  30)
- Region (North America, Europe)
- Smoking status (Never, Current, Former)
- Lumbar spine BMD T-score at baseline ( $\leq$  -2.5,  $>$  -2.5)
- Total hip BMD T-score at baseline ( $\leq$  -2.5,  $>$  -2.5)
- Femoral neck BMD T-score at baseline ( $\leq$  -2.5,  $>$  -2.5)
- Prior clinical fractures (Yes = Subjects with a record in medical history with “fracture” in the preferred term, No)
- Prevalent vertebral fractures (Yes = Subjects with any vertebral fracture with a Genant semi-quantitative score  $>$  0, No)
- Prior Fracture (Yes = Subjects with a prevalent vertebral fracture and /or a prior clinical fracture, No)
- s-PINP at baseline (tertile values calculated based on ITT population )

### **3.9. Anti-Abaloparatide Antibody Status**

At Day 1, Day 14, Month 1, Month 3, Month 6, Month 9, Month 12/EOT, and Month 13/EOS, the anti-abaloparatide antibody (ADA) assessment in the serum samples for immunogenicity testing will be categorized by two outcomes:

- Negative for the ADA (ADA-)
- Positive for the ADA (ADA+)

For those subjects with a positive ADA (i.e., ADA is present), the serum samples will be further assessed for the presence of neutralizing anti-abaloparatide antibodies (NAb), and the results will be categorized by two outcomes:

- Negative for the NAb (NAb-)
- Positive for the NAb (NAb+)

Subject ADA status and presence of NAb by Month 12 (ADA-, ADA+/NAb+, ADA+/NAb-, All ADA+) will be defined as follows:

- Subjects will be classified as ADA- if they were ADA- in all post-baseline immunogenicity assessments during the 12-month treatment period.
- Subjects will be classified as ADA+ and NAb+ if they were ADA+ at any post-baseline immunogenicity assessment and NAb+ at any subsequent tests during the 12-month treatment period.
- Subjects will be classified as ADA+ and NAb- if they were ADA+ at any post-baseline immunogenicity assessment and NAb- at all subsequent tests during the 12-month treatment period.

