- 9. X-ray results will be evaluated by a qualified evaluator at the site, with prevalent fractures assessed using the Genant-semiquantitative scoring method.
- 10. Serum calcium and albumin will be measured predose from the standard chemistry panel on Screening, Day 1, Month 1 and Month 6 and from a separate blood draw predose at Month 3 and Month 9 and at 4 hours postdose at Month 1. Albumin corrected serum calcium will be reported using the serum calcium and albumin results on the following visits: Screening, Day 1, Month 1, Month 3, Month 6 and Month 9.
- 11. A 24-hour urine collection will be collected at Day 1 and Month 3 and will be used for urinary calcium and urinary creatinine measurements. Subjects will discard the 1st void and begin a 24-hour urine collection on the day prior to the study site visit.
- 12. Spine radiographs at screening will be assessed locally. If the subject reports that a fracture has occurred, remind the subject to bring X-rays and any medical reports of the fracture to the next study site visit. Documentation must be obtained on all new fractures that occur during the study. This documentation should be maintained in the source documents.
- 13. Each DXA for a given subject should be performed on the same machine, and if available, preferably by the same technician and will be assessed by a central imaging laboratory. For screening purposes, DXA scans of the lumbar spine, total hip, and femoral neck taken up to 35 days prior to the beginning of the Screening Period may be used to enroll a subject in the study if the BMD T-score criteria in Section 6.2.5 are met.
- 14. Samples for ADA will be drawn prior to treatment on Day 1, Day 14, Month 1, Month 3, Month 6, Month 9, Month 12/EOT, and 1 month following the last dose of study drug. All subjects who remain antibody positive will continue to be followed for ADA testing every 6 months until the result is negative.

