6.5.3. Anti-Drug Antibody Testing

Serum samples for ADA testing will be collected predose at Day 1, Day 14, Month 1, Month 3, Month 6, Month 9, Month 12, and 30 days following the last dose of study drug. Samples should be taken prior to in-office administration to prevent interference with the ADA assay. Samples will be tested for the presence of binding ADAs, including determination of antibody titer. Any positive samples will be tested for the potential to neutralize abaloparatide in a cell-based assay. Additionally, positive samples will be tested for cross reactivity to endogenous PTH and PTHrP. Any subject who show presences of antibodies at EOT will be retested at 6-month intervals post-study until antibody status returns to negative.

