## **2. SUBJECT ANALYSIS POPULATIONS**

### **2.1. Population Definitions**

Five subject populations will be considered in the statistical analyses of this study.

- Intention-to-Treat (ITT) population**

The ITT population consists of all subjects randomized into this study.

- Modified Intention-to-Treat (mITT) population**

The mITT population includes all randomized subjects who received at least one dose of study drug and had a baseline lumbar spine BMD measurement and at least one post-baseline lumbar spine BMD measurement.

- Safety population**

The Safety population consists of all randomized subjects who received at least one dose of study drug.

- Per-Protocol (PP) population**

The PP population consists of all mITT subjects who did not have any critical protocol deviations (described in [Section 2.2](#)).

- Antibody Population**

The Antibody population will include subjects in the Safety population who have at least one post-baseline anti-drug antibody assessment.

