#### **4.4.1.4. Analysis by Anti-Abaloparatide Antibody Status**

The analysis of the primary efficacy endpoint using MMRM model will also be repeated for the Antibody population within each treatment group, in which the subjects who are ADA+ at any post-baseline time point will be compared with subjects who are ADA- at all post-baseline time points. The MMRM model will include the fixed effects of ADA status, DXA instrument manufacturer, visit, and ADA status-by-visit interaction, with the baseline lumbar spine BMD as covariate.

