#### **4.6.3. Anti-Drug Antibody**

The ADA assessment in the serum samples for immunogenicity testing will be categorized by 2 outcomes:

- Negative for anti-drug antibodies
- Positive for anti-drug antibodies

The number (%) of subjects in the above categories of abaloparatide antibodies will be summarized at Day 1 (Visit 3), Day 14 (Visit 4), Month 1 (Visit 5), Month 3 (Visit 7), Month 6 (Visit 10), Month 9 (Visit 13), Month 12/EOT (Visit 16), and 30 days following the last dose of study drug (Month 13/Visit 17/EOS) by treatment group using the Antibody population.

For those subjects with anti-abaloparatide antibody present (i.e., are ADA positive), the titer level, the presence of neutralizing anti-abaloparatide antibodies (negative or positive), and the assessment outcomes for cross-reactivity to parathyroid hormone (PTH) (negative or positive) and parathyroid hormone-related peptide (PThrP) antibodies (negative or positive) together with the neutralizing antibody status in subjects that are positive for PTH (negative or positive for the presence of PTH-neutralizing antibodies) or PThrP (negative or positive for the presence of PThrP-neutralizing antibodies) will be summarized by study visit. Figures for the incidence of antibody and neutralizing antibody for the anti-abaloparatide, anti-PTH, and anti-PThrP will be presented by nominal visit.

All antibody information will be presented in a data listing.

The results of antibody analyses will be presented in a separate report.

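### Subject-level ADA status ignores the pre-dose Day 1 sample, so women positive on Day 1 and again on treatment are pooled with newly positive women in all analyses by ADA status

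*SAP*

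**What the plan says.** SAP 3.9 lists Day 1 among the antibody assessments, then builds all three subject-level classes without it:

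- ADA-: "Subjects will be classified as ADA- if they were ADA- in all post-baseline immunogenicity assessments during the 12-month treatment period".
- ADA+/NAb+: "Subjects will be classified as ADA+ and NAb+ if they were ADA+ at any post-baseline immunogenicity assessment and NAb+ at any subsequent tests".
- ADA+/NAb-: "Subjects will be classified as ADA+ and NAb- if they were ADA+ at any post-baseline immunogenicity assessment and NAb- at all subsequent tests".

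The baseline sample exists. Footnote 14 to the protocol's schedule (Table 1) states: "Samples for ADA will be drawn prior to treatment on Day 1, Day 14", and so on through the study. Protocol 6.5.3 adds: "Samples will be tested for the presence of binding ADAs, including determination of antibody titer".

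The Antibody population in SAP 2.1 neither removes nor separates Day 1 positives: "The Antibody population will include subjects in the Safety population who have at least one post-baseline anti-drug antibody assessment". SAP 4.4.1.4 makes the same split for lumbar spine BMD within each arm, where "the subjects who are ADA+ at any post-baseline time point will be compared with subjects who are ADA- at all post-baseline time points"; its model has no term for Day 1 status. Status defined this way is also used in SAP 4.2 (baseline characteristics), 4.3.1 (exposure and compliance), 4.4.2 (total hip and femoral neck BMD), 4.6.1 (TEAEs) and 4.6.2 (AESIs).

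**The concern.** Antibody present before the first dose cannot have been caused by the study drug. The rule does not distinguish a woman whose reactivity was there on Day 1 and did not change from one who became positive on treatment. If the two kinds of antibody differ in effect, the ADA+ group is a mixture, and its contrast with ADA- describes neither kind.

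The SAP uses baseline information for comparable safety classifications. In 4.6.1 an adverse event counts as treatment-emergent only if it is new or has worsened since dosing began. In 4.6.5.1 and 4.6.6.1, subjects whose laboratory or vital-sign value was already potentially clinically significant at baseline are left out of numerator and denominator. ADA status has no such rule, although the baseline data are collected.

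At stake is the reading of the analyses meant to show whether antibody affects BMD, adverse events or exposure.

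**Working it through.** **Step 1. Apply the SAP 3.9 rule case by case.**

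| Day 1 | On-treatment samples | SAP class |
|---|---|---|
| Negative | All negative | ADA- |
| Negative | At least one positive | ADA+ |
| Positive | At least one positive | ADA+, with or without a titer rise |
| Positive | All negative | ADA- |
| Missing | Any | Set by on-treatment samples; no rule for the missing baseline |

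Rows 2 and 3 are pooled. Day 1 positivity alone does not make a woman ADA+ (row 4).

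**Step 2. Size.** The plan has no figure to reproduce: it gives no Day 1 prevalence, no expected ADA incidence and no assumed effect of ADA on BMD. The values below are assumptions.

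- b = share positive on Day 1 (1% to 10%)
- p = share of those positive again on treatment (0.5 or 1)
- i = share of Day 1 negatives who become positive (10% to 80%)

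ADA+ rate under the SAP: R = (1 - b)i + bp. Pre-existing share of the ADA+ group: f = bp / R. If pre-existing antibody is inert and no Day 1 positive has a titer rise, the ADA+ versus ADA- contrast keeps 1 - f of its size.

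| b | i | p | R | f | Contrast kept |
|---|---|---|---|---|---|
| 1% | 80% | 0.5 | 79.2% + 0.5% = 79.7% | 0.6% | 99.4% |
| 2% | 20% | 1 | 19.6% + 2.0% = 21.6% | 9.3% | 90.7% |
| 5% | 20% | 0.5 | 19.0% + 2.5% = 21.5% | 11.6% | 88.4% |
| 5% | 10% | 1 | 9.5% + 5.0% = 14.5% | 34.5% | 65.5% |
| 10% | 10% | 1 | 9.0% + 10.0% = 19.0% | 52.6% | 47.4% |

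The first and last rows are the extremes of the range. The pooled women are bp of all subjects, from 0.5% to 10%. Of 237 randomized per arm that is 0.005 × 237 = 1.2 to 0.10 × 237 = 23.7 women.

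**Step 3. Dependence on the inert assumption.** If pre-existing antibody has a fraction r of the induced effect, the contrast kept is 1 - f(1 - r). With f = 34.5%, r = 0.5 keeps 1 - 0.345 × 0.5 = 82.8%; r = 1 keeps 100%; r above 1 enlarges the contrast.

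**Step 4. Direction of the ADA+ rate.** R always exceeds the newly positive share of all subjects by bp. Against incidence among Day 1 negatives, R - i = b(p - i). With b = 5% and p = 0.5 this is +1.5 points at i = 20% (21.5% v 20%), zero at i = 50%, and -1.5 points at i = 80% (78.5% v 80%).

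**The case against.** The strongest defence is that the rule answers a legitimate question: does antibody present on treatment, whatever its origin, go with a different BMD or safety outcome? The SAP never calls its ADA+ class drug-induced. SAP 4.6.3 tabulates Day 1 positivity by arm, summarizes titer by visit among positives and lists all antibody data, so the baseline rate is visible and the split could be made later. Exclusion criterion 16 bars prior PTH- and PTHrP-derived drugs, which makes drug-raised antibody on Day 1 less likely. Antibody results go into a separate report.

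All of this stands, and it limits the size of the problem. It does not remove the pooling. A by-visit count takes nobody out of the ADA+ group in the BMD, TEAE or AESI analyses, and a split made later from the listings would be unplanned. Criterion 16 does not exclude reactivity that no drug has raised, and the plan itself tests and reports Day 1.

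Four stronger readings are tempting and are not supported:

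- That every Day 1 positive is classed ADA+. Row 4 of the first table shows otherwise.
- That drug-induced immunogenicity is overstated. The class carries no such label, and Step 4 shows that the rate can lie on either side of incidence in Day 1 negatives.
- That an sMTS to SC comparison of ADA incidence is pulled towards equality. No ratio or test of that kind is planned; the BMD contrasts by status are made within each arm.
- That all the ADA+ versus ADA- comparisons are diluted. That needs antibody that persists and has less effect than induced antibody.

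**Conclusion.** The concern holds as a gap in a definition. Day 1 status is unused, no treatment-emergent or boosted ADA is defined, and women positive both before and during treatment are analysed with the newly positive.

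The consequence is conditional: the within-arm contrasts are weakened only if pre-existing antibody persists and has less effect than induced antibody. How much is unknown. The 47% to 99% range rests wholly on assumed prevalence, persistence and incidence, on inert pre-existing antibody, and on no titer rise among Day 1 positives. Any Day 1 positives with a true rise belong in the ADA+ group and would reduce the loss.

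The primary non-inferiority test is untouched: its model in SAP 4.4.1.1 has no ADA term and its population does not depend on ADA status. The point is of minor to moderate weight, but worth settling before the antibody data are analysed, because the correction needs no new data.

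**What to change.** In SAP 3.9, add a treatment-emergent ADA flag: negative on Day 1 and positive at any post-baseline sample in the treatment period, or positive on Day 1 with a titer rise of a size fixed in advance from the assay's properties. State how a missing Day 1 sample is handled; Table 1 schedules no screening ADA sample to stand in for it. Show Day 1 positives as a separate category.

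Use the flag in 4.4.1.4, 4.4.2, 4.6.1 and 4.6.2. Keep the present any-post-baseline-positive class as a supportive analysis, so that the question about antibody of any origin is still answered.

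The cost is one more derived variable, a titer threshold to agree, and slightly smaller ADA+ groups with somewhat less precise contrasts. No extra sampling is needed, and the antibody analyses are already reported separately.

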### **3.10. Withdrawals, Dropouts, and Loss to Follow-up**

Subjects who are withdrawn or discontinue from the study will not be replaced.

### **3.11. Missing, Unused, and Spurious Data**

Statistical methods for addressing missing data for the analyses of the primary and secondary efficacy endpoints are described in [Section 4.4](#).

Rules for imputation of missing dates for onset of AEs and start dates of concomitant medications are included in [Appendix A](#) of this SAP. Unless otherwise specified, missing dates for onset of AEs and start of concomitant medications will be handled according to the imputation rules.

In the event that incorrect data are discovered after database lock, the impact of such incorrect data will be assessed and a determination will be made as to whether the data need to be corrected in the database (and subsequently in the analysis). In cases where it is decided that the data need to be corrected, this decision will be documented, and the documentation will be saved in the Trial Master File.

All available data will be included in data listings.

### **3.12. Visit Windows**

In general, the nominal visit will be used for all efficacy and safety data summaries and analyses.

During the COVID-19 pandemic, if a subject's DXA assessment cannot be performed during the protocol specified visit windows, the site will contact the study Medical Monitor, and the subject will be allowed to make up the visits within an allowed time period. The allowable time period for collection of DXA assessments is shown in [Table 2](#), where the ideal visit day is defined as the ideal number of days from Day 1, when the first dose of study drug was administered, to the nominal visit.

**Table 2: Allowable Time Period for Collection of BMD Assessments**

Month	Ideal Visit Day	BMD Assessment
Month 3	90	Up to 30 days after ideal visit day
Month 6	180	Up to 120 days after ideal visit day
Month 12	360	± 4 days of the ideal visit day

Due to the expanded time periods for collection of efficacy assessments, analysis visit windows are defined in [Table 3](#) for the analyses of BMD and serum markers of bone metabolism (s-PINP and s-CTX) data to determine the assessment that will be used for a given study visit.

**Table 3: Analysis Visit Windows for BMD, s-PINP and s-CTX Assessments**

Scheduled Visit / Month	Ideal Visit Day	Visit Window in Study Days	
		BMD	s-PINP and s-CTX
Visit 3 / Baseline	$\leq 1$	$\leq 1$	$\leq 1$
Visit 4 / Month 1	30		2-60
Visit 5 / Month 3	90	2 -120	61-120
Visit 6 / Month 6	180	121 - 300	121-300
Visit 8 / Month 12	360	$\geq 301$	$\geq 301$

It is possible that more than 1 assessment for a parameter may be obtained within the same analysis visit window. In such circumstances, the assessment with the date closest to the ideal visit day will be used. In the event that 2 assessments are equidistant to the ideal visit day, the later of the assessments will be used.

The analysis visit window convention will not be applied to the data listings. The data listings will display all data as collected with the corresponding nominal visit.

### **3.13. Interim Analyses**

No interim analysis for efficacy is planned for this study.

#### **4. STUDY ANALYSES**

##### **4.1. Subject Disposition**

Subject disposition will be tabulated by treatment group, including the number screened, the number randomized, the number treated, the number in each analysis population, the number who completed the study, the number who discontinued study drug with the primary reason for discontinuation of the treatment, and the number who discontinued from the study together with the primary reason for discontinuation as recorded in the eCRF. The number of subjects excluded from the PP population together with the exclusion reasons will also be summarized.

A Kaplan-Meier plot of the time from randomization to withdrawal from study will be presented by treatment group. Subjects who complete the study will be censored at their date of study completion as recorded on the EOS eCRF page.

The total number of subjects randomized will also be tabulated by region (North America, Europe), country, study site, and treatment group.

Subject disposition data will be carefully reviewed with respect to the impact of the COVID-19 pandemic on study conduct. A summary of subject disposition by subject's randomization date relative to COVID-19 pandemic onset (subjects randomized prior to 01 March 2020 vs subjects randomized on or after 01 March 2020) will be presented. The number (%) of subjects with assessments impacted by COVID-19 as recorded on the COVID-19 Impact Log eCRF page will be summarized by visit and by category. The categories are:

- Altered Protocol Assessment/Procedure
- Discontinuation
- IP – Missed/Modified
- Missing Data
- Missed Visit
- Out of Window Visit
- Remote /Virtual Visit
- Assessment Not Done
- Other

A listing of subjects with assessments impacted by COVID-19 as indicated on the COVID-19 Impact Log eCRF page will be provided. The listing will include subject ID, age, race, site, visit, CRF form used, impact category, and comment.

A by-subject data listing of study completion information, including the primary reasons for premature study withdrawal as recorded in the eCRF, will be presented. A by-subject data listing of subjects excluded from PP population and the reasons for exclusion will also be presented.

A summary of screening failures and listings of inclusion/exclusion criteria responses for screening failure subjects will also be presented.

##### **4.2. Demographics and Baseline Characteristics**

Demographic and baseline characteristics will be summarized and presented by treatment group and overall for the mITT, ITT, PP and Safety populations. These data include:

- Age, age group (<65, 65-<75,  $\geq$ 75 years), race, ethnicity, region (North America, Europe), height, weight, body mass index (BMI), and BMI group (BMI<25,  $25 \leq$ BMI<30, BMI $\geq$ 30). Subjects who report more than one race category will be counted under the race category “Multiple”.
- Smoking, drinking status and other substances use:
  - Smoking status (Never, Current, Former): Smoking status is based on the two questions asked during screening: ‘Has the subject ever smoked cigarettes?’ and ‘Has the subject ever smoked tobacco?’ If both are answered ‘Never’, then smoking status is ‘Never’. If either one is answered ‘Current’, then smoking status is ‘Current’. If either question is answered ‘Former’ and the answer to the other question is not ‘Current’, then smoking status is ‘Former’.)
  - Has the subject ever smoked cigarettes? (Never, Current, Former)
    - Number of cigarettes per day
    - Number of years smoked
  - Has the subject ever smoked tobacco? (Never, Current, Former),
    - ‘How long ago did you stop?’
  - Has the subject ever drunk alcohol? (Never, Current, Former)
    - Number of years of drinking alcohol
    - How many drinks per week?
  - Has the subject ever used other substances? (Never, Current, Former).
- Fracture history of:
  - Prior clinical fracture (Yes, No): Yes - for any subjects with a record in medical history with “fracture” in the preferred term. No - otherwise.
  - Prevalent vertebral fracture (Yes, No): Yes - for any subjects with any vertebra with a Genant semi-quantitative score  $> 0$  on the Spine X-ray Evaluation eCRF page. No - otherwise.
  - Prior fracture (Yes, No): Yes -for any subjects with a prevalent vertebral fracture and/or a prior clinical fracture. No - otherwise.
  - Prior clinical vertebral fracture (Yes, No): Yes -for any subjects with a record in medical history with "vertebral fracture" or "spinal fracture" in the preferred term. No - otherwise.
  - Prior vertebral fracture (Yes, No): Yes -for any subjects with a prior clinical vertebral fracture or a prevalent vertebral fracture. No - otherwise.
- Baseline values of BMD measurements and biomarker parameters including:
  - Lumbar spine BMD T-score and T-score group ( $\leq -2.5$ ,  $> -2.5$ )
  - Total hip BMD T-score and T-score group ( $\leq -2.5$ ,  $> -2.5$ )
  - Femoral neck BMD T-score and T-score group ( $\leq -2.5$ ,  $> -2.5$ )
  - s-PINP and s-PINP category (tertile values calculated based on ITT population)
  - s-CTX.

The continuous variables including age (years), height (cm), weight (kg), BMI (kg/m^2), number of years smoked cigarettes, number of cigarettes per day, number of years of drinking alcohol, number of drinks per week, s-PINP, s-CTX and BMD T-score will be summarized using descriptive statistics (number of subjects, mean, SD, median, interquartile range, minimum and maximum). The categorical variables including ethnicity and race, subgroups (see [Section 3.8](#)) of baseline BMD measurements, history of fracture and fracture location, baseline s-PINP category, and history of use of cigarettes, tobacco, alcohol, and other substances will be presented by the number and percentage of subjects.

Medical history will be presented by MedDRA system organ class (SOC), preferred term (PT), and treatment group, summarizing the proportion of subjects in each treatment group who have a condition noted.

Physical examination results at baseline will be summarized by body system as recorded in the eCRF and treatment group.

No statistical tests will be performed for the demographic and baseline variables.

All analyses described in this section will also be repeated for the Antibody population. The presentation of these analyses will be based on subjects' ADA status and presence of neutralizing antibody (NAb) during the study with columns for ADA-, ADA+/NAb+, ADA+/NAb-, All ADA+, and Overall.

Additionally, demographics data and baseline characteristics will be tabulated by all subgroups listed in [Section 3.8](#) using the ITT, mITT and PP populations. To address the effect of the COVID-19 pandemic, summaries of demographic data and baseline characteristics by subject's randomization date relative to COVID-19 pandemic onset (subjects randomized prior to 01 March 2020 vs subjects randomized on or after 01 March 2020) will be presented using the ITT and mITT populations.

Demographics including race, ethnicity, age, and country for screen failure subjects will also be summarized descriptively.

All subject data collected for demographics and baseline characteristics will be presented by treatment, study site, and subject number in data listings.

